8.1.6 Interim Analyses and Data Monitoring

No interim analysis or data monitoring is planned for this study.

8.1.7 Multicenter Studies

The clinical study will be conducted under a common protocol for each investigational site with the intention of pooling all the data for analysis. Every effort will be made to promote consistency in study execution at each study site.

8.1.8 Multiple Comparisons/Multiplicity

No adjustments for multiple comparisons or multiplicity will be made.

8.1.9 Use of an Efficacy Subset of Subjects

Not applicable to this study.

8.1.10 Active-Control Studies Intended to Show Equivalence

Not applicable to this study.

8.1.11 Examination of Subgroups

Not applicable to this study.

8.2 Disposition of Subjects

The number of subjects included in the Safety population will be summarized for all subjects, for subjects that received S5G4T-1 in 54-01/54-02, and for subjects that received vehicle in 54-01/54-02. The number of subjects enrolled, completed, and discontinued (including the reasons for discontinuation) will be summarized similarly.

Subjects who are excluded from the Safety population will be summarized by the reasons for exclusion.

8.3 Protocol Deviations

All protocol deviations will be reported to the sponsor and recorded throughout the study. Protocol deviations will not be entered into the database. SolGel will provide a list of protocol deviations to QST. A tabulation of protocol deviations will be presented in a data listing.

8.4 Data Sets Analyzed

Subjects will be presented/summarized based on the primary reason for exclusion.

8.4.1 Safety Population

All analyses will be performed using the Safety Population of the study. All patients who receive at least one confirmed dose of S5G4T-1 and have at least one assessment will be included in the Safety Population.

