12. STUDY POPULATION

Each patient who signs an informed consent and meets Entry Criteria or Inclusion/Exclusion Criteria will be enrolled in the study. Patients will receive study product in an open-label fashion (see instructions in [Section 13.4](#)) for entire trial period (i.e., the treatment assignment, E-BPO, 5% Cream (Encapsulated Benzoyl Peroxide Cream, 5%, S5G4T-1), will be known to the patient, to study personnel, Sol-Gel personnel and its representatives.

12.1. Entry Criteria (only applies for patients entering from Phase 3, SGT-54-01 or SGT-54-02)

To be included in the study, patients must meet the following eligibility /inclusion criteria:

1. Patient must sign an Institutional Review Board (IRB) approved written informed consent for the extension study.
2. Complete 12-week or within the week 12 window time (± 4 days) of the double-blind treatment period of study SGT-54-01 or Study SGT-54-02 and missed not more than one visit of Visits 3, 4 or 5 in Study SGT-54-01 or Study SGT-54-02.
3. Patients who in the opinion of the investigator, are likely to be able to follow the restrictions of the protocol and complete the study.

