18.2. Populations Analyzed

All analyses will be performed using the Safety Population of the study. Part of this population will be referred as the extension safety population, and part as a new enrolled safety population. All patients who receive at least one confirmed dose of S5G4T-1 (in either Study SGT-54-01 or Study SGT-54-02, and in this study or for new patients in this study) and have at least one assessment will be included in the Safety Population.

The number of patients included in the Safety Population will be summarized.

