8. STATISTICAL AND ANALYTICAL PLANS

8.1 General Methodology

All statistical processing will be performed using SAS® version 9.4 or later unless otherwise stated.

Descriptive statistics will be used to provide an overview of the efficacy and safety results. For categorical parameters, the number and percentage of subjects in each category will be presented. For continuous parameters, descriptive statistics will include n (number of subjects), mean, standard deviation (SD), median, minimum (min) and maximum (max).

No inferential testing or imputations for missing data will be performed. No interim analyses are planned.

All analyses will be performed using the Safety Population of the study.

Where applicable the analysis will be presented by overall treatment group in 54-07 as well as by treatment group assignment in 54-01/54-02.

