10. CHANGES IN THE PLANNED ANALYSES

The protocol was written in a way that subjects who did not participate in 54-01 or 54-02 could be enrolled into 54-07. When the SAP was created, 54-07 was fully enrolled, and no subject was enrolled who did not complete the 54-01 or 54-02 study. The SAP was written such that any text from the protocol that discusses the new subjects was excluded.

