Table 14.3.1.4.1: Summary of Treatment-Emergent Serious Adverse Event Characteristics (Safety Population).....	82
Table 14.3.1.4.2: Summary of Treatment-Emergent Serious Adverse Events by MedDRA System Organ Class and Preferred Term (Safety Population).....	84
Table 14.3.1.4.3: Summary of Serious Treatment-Emergent Adverse Events by Severity (Safety Population)	85
Table 14.3.1.4.4: Summary of Treatment-Emergent Serious Adverse Events by Relationship to Study Drug (Safety Population)	86
Table 14.3.1.5.1: Summary of Treatment-Emergent Serious Adverse Event Characteristics – By Period (Safety Population)	87
Table 14.3.1.5.2: Summary of Treatment-Emergent Serious Adverse Events by MedDRA System Organ Class and Preferred Term – By Period (Safety Population)	89
Table 14.3.1.5.3: Summary of Treatment-Emergent Serious Adverse Events by Severity – By Period (Safety Population)	90
Table 14.3.1.5.4: Summary of Treatment-Emergent Serious Adverse Events by Relationship to Study Drug – By Period (Safety Population).....	91
Table 14.3.1.4.1: Summary of Vital Signs (Safety Population)	92

**Table 14.0.1: Summary of Subject Completion/Discontinuation
(All Enrolled Subjects)**

	SGT-54-01/SGT-54-02 Vehicle Cream (N=xxx)	SGT-54-01/SG-54-02 E-BPO 5% Cream (N=xxx)	SGT-54-07 E-BPO 5% Cream (N=xxx)
Completed Study			
Yes	xx (xx.x%)	xx (xx.x%)	xx (xx.x%)
No	xx (xx.x%)	xx (xx.x%)	xx (xx.x%)
Reason for Discontinuation			
Adverse Event	xx (xx.x%)	xx (xx.x%)	xx (xx.x%)
Lost to Follow-Up	xx (xx.x%)	xx (xx.x%)	xx (xx.x%)
Lack of Efficacy	xx (xx.x%)	xx (xx.x%)	xx (xx.x%)
Pregnancy	xx (xx.x%)	xx (xx.x%)	xx (xx.x%)
Protocol Violation	xx (xx.x%)	xx (xx.x%)	xx (xx.x%)
Withdrawal by Subject	xx (xx.x%)	xx (xx.x%)	xx (xx.x%)
Study Terminated by Sponsor	xx (xx.x%)	xx (xx.x%)	xx (xx.x%)
Physician Decision	xx (xx.x%)	xx (xx.x%)	xx (xx.x%)
Worsening of Condition	xx (xx.x%)	xx (xx.x%)	xx (xx.x%)
Other	xx (xx.x%)	xx (xx.x%)	xx (xx.x%)

SOURCE: USERNAME\SPONSOR\PROJECT\JOBNAME (DATE, TIME)

**Table 14.0.2.1: Summary of Subject Enrollment and Evaluability
(All Enrolled Subjects)**

	SGT-54-01/SGT-54-02 Vehicle Cream (N=xxx)	SGT-54-01/SG-54-02 E-BPO 5% Cream (N=xxx)	SGT-54-07 E-BPO 5% Cream (N=xxx)
Number of Subjects Included in the Safety Population	xx (xx.x%)	xx (xx.x%)	xx (xx.x%)
Number of Subjects Excluded from the Safety Population	xx (xx.x%)	xx (xx.x%)	xx (xx.x%)
Reasons Excluded from the Safety Population ^a			
No Documented use of Study Drug	xx (xx.x%)	xx (xx.x%)	xx (xx.x%)

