No Post Baseline Safety Assessment	xx (xx.x%)	xx (xx.x%)	xx (xx.x%)

^a Table includes primary reason (assigned in order presented in table) for reason subject was excluded.

SOURCE: USERNAME\SPONSOR\PROJECT\JOBNAME (DATE,TIME)

**Table 14.1.1.1: Summary of Subject Demographic Characteristics
(Safety Population)**

	SGT-54-01/SGT-54-02 Vehicle Cream (N=xxx)	SGT-54-01/SG-54-02 E-BPO 5% Cream (N=xxx)	SGT-54-07 E-BPO 5% Cream (N=xxx)
Age (years)			
n	xx	xx	xx
Mean	xx.x	xx.x	xx.x
SD	xx.xx	xx.xx	xx.xx
Median	xx.x	xx.x	xx.x
Min. to Max.	xx to xx	xx to xx	xx to xx
Sex			
n	xx	xx	xx
Male	xx (xx.x%)	xx (xx.x%)	xx (xx.x%)
Female	xx (xx.x%)	xx (xx.x%)	xx (xx.x%)
Ethnicity			
n	xx	xx	xx
Hispanic or Latino	xx (xx.x%)	xx (xx.x%)	xx (xx.x%)
Not Hispanic or Latino	xx (xx.x%)	xx (xx.x%)	xx (xx.x%)
Not Reported/Unknown	xx (xx.x%)	xx (xx.x%)	xx (xx.x%)
Race			
n	xx	xx	xx
American Indian or Alaska Native	xx (xx.x%)	xx (xx.x%)	xx (xx.x%)
Asian	xx (xx.x%)	xx (xx.x%)	xx (xx.x%)
Black or African American	xx (xx.x%)	xx (xx.x%)	xx (xx.x%)
Native Hawaiian or Other Pacific Islander	xx (xx.x%)	xx (xx.x%)	xx (xx.x%)
White	xx (xx.x%)	xx (xx.x%)	xx (xx.x%)
Multiple/Other ^a	xx (xx.x%)	xx (xx.x%)	xx (xx.x%)

^a See Listing 16.2.4.1 for a complete list of other races.

SOURCE: USERNAME\SPONSOR\PROJECT\JOBNAME (DATE,TIME)

Table 14.1.2.1: Subject Baseline Characteristics
(Safety Population)
(Page 1 of 2)

	SGT-54-01/SGT-54-02 Vehicle Cream (N=xxx)	SGT-54-01/SG-54-02 E-BPO 5% Cream (N=xxx)	SGT-54-07 E-BPO 5% Cream (N=xxx)
Height (cm)			
n	xx	xx	xx
Mean	xx.x	xx.x	xx.x
SD	xx.xx	xx.xx	xx.xx
Median	xx.x	xx.x	xx.x
Min. to Max.	xx to xx	xx to xx	xx to xx
Weight (kg)			
n	xx	xx	xx
Mean	xx.x	xx.x	xx.x
SD	xx.xx	xx.xx	xx.xx
Median	xx.x	xx.x	xx.x
Min. to Max.	xx to xx	xx to xx	xx to xx
BMI (kg/m²)			
n	xx	xx	xx
Mean	xx.x	xx.x	xx.x
SD	xx.xx	xx.xx	xx.xx
Median	xx.x	xx.x	xx.x
Min. to Max.	xx to xx	xx to xx	xx to xx

SOURCE: USERNAME\SPONSOR\PROJECT\JOBNAME (DATE,TIME)

Table 14.1.2.1: Subject Baseline Characteristics
(Safety Population)
(Page 2 of 2)

	SGT-54-01/SGT-54-02 Vehicle Cream (N=xxx)	SGT-54-01/SG-54-02 E-BPO 5% Cream (N=xxx)	SGT-54-07 E-BPO 5% Cream (N=xxx)
Inflammatory Lesion Count			
n	xx	xx	xx
Mean	xx.x	xx.x	xx.x
SD	xx.xx	xx.xx	xx.xx
Median	xx.x	xx.x	xx.x
Min. to Max.	xx to xx	xx to xx	xx to xx
Investigator Global Assessment			
n	xx	xx	xx
0 - Clear	xx (xx.x%)	xx (xx.x%)	xx (xx.x%)
1 - Almost Clear	xx (xx.x%)	xx (xx.x%)	xx (xx.x%)
2 - Mild	xx (xx.x%)	xx (xx.x%)	xx (xx.x%)

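### The assessment condition in the Safety Population is either redundant or able to drop a former vehicle patient with a reported adverse event; it should be deleted

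*SAP*

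**What the plan says.** - SAP 8.4.1 sets two conditions: patients who have had a confirmed dose of S5G4T-1 and "have at least one assessment will be included in the Safety Population". Protocol 18.2 and the protocol synopsis carry the same second condition ("and have at least one assessment will be included in the Safety Population"). None of these texts says that the assessment must be post-baseline, and none defines assessment.
- The Table 14.0.2.1 shell gives two reasons for exclusion, assigned in order: first "No Documented use of Study Drug", then "No Post Baseline Safety Assessment".
- The population governs everything: "All analyses will be performed using the Safety Population of the study" (SAP 8.1).
- Only rollovers are in the study. SAP Section 10 records that "no subject was enrolled who did not complete the 54-01 or 54-02 study". Protocol 12.1 requires that they completed Week 12 of the parent trial and "missed not more than one visit of Visits 3, 4 or 5 in Study SGT-54-01 or Study SGT-54-02".
- SAP 8.1.2 places Baseline before the first application in 54-01/54-02. Under SAP 8.1.3, parent-trial data of former S5G4T-1 patients enter the 54-07 summaries. Under SAP 8.9.2, parent-trial adverse events of former vehicle patients are pre-treatment.
- In the by-period shells (14.3.1.3.x and 14.3.1.5.x), the denominator is the Safety Population patients who finish the period plus those who have an event in it.

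**The concern.** Safety is the study's only stated objective, and inclusion in its one analysis set may depend on what happens after dosing. Former vehicle patients meet S5G4T-1 for the first time in 54-07, and their first scheduled follow-up is Day 29 ± 10. Someone who stops early because of a local reaction is also someone who may have no later visit.

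The protocol foresees events that become known outside a visit: Section 16.4 accepts spontaneous patient reports, and Section 13.2 provides follow-up contacts after discontinuation for an adverse event. Because the shell separates lack of documented use from lack of an assessment, a patient with documented exposure can be excluded on the second ground alone. A recorded event would then be missing from the treatment-emergent tables.

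**Working it through.** The plan has no figure to reproduce here. SAP Section 9 bases the sample size on a minimum requirement and gives no event or dropout rate. The check is a reading of the rules, followed by bounds.

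**Who can be excluded under the second reason**

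| Patient | Literal reading (Baseline from 54-01/54-02) | Post-dosing reading |
|---|---|---|
| Former S5G4T-1 | Kept: parent-trial visits are post-baseline | Kept: parent-trial visits also follow S5G4T-1 dosing |
| Former vehicle, seen after first S5G4T-1 dose | Kept | Kept |
| Former vehicle, documented use, no later visit | Kept: parent Week 12 visit is post-baseline | Excluded, unless a reported event counts as an assessment |

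Only the last cell matters, and the documents do not say which column applies. A related point is also open: SAP 8.1.3 leaves early termination and unscheduled visits before Day 22 unanalysed, without saying whether such a visit satisfies 8.4.1.

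**Direction of the effect**

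Let N be the dosed patients, k those excluded, x the patients with events among the N − k kept, and m the excluded patients with a reported event (0 ≤ m ≤ k).

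- Overall tables: the planned rate is x/(N − k), and the all-dosed rate is (x + m)/N. The all-dosed rate is higher only if m/k > x/(N − k).
- By-period tables: an excluded patient without an event would not be counted anyway, because that patient neither finishes the period nor has an event. With D the planned denominator, restoring the others turns x/D into (x + m)/(D + m). This is higher whenever m > 0 and x < D. Here the condition can remove only patients with events.

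**Size, by assumption only**

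N = 700 is the planned enrolment, used as the dosed number. The documents do not give the vehicle share (assumed 25% to 50%, or 175 to 350 patients) or the share of these never seen again (assumed 1% to 5%). Then k runs from 175 × 0.01 = 1.75 (about 2) to 350 × 0.05 = 17.5 (about 18). The patients whose events are lost, m, are a subset and may be none. Reported rates near 2%, 7% and 22% are taken from the background sections as illustrations.

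| k | Planned overall rate | All-dosed, m = 0 | All-dosed, m = k (extreme) |
|---|---|---|---|
| 2 | 14/698 = 2.0% | 14/700 = 2.0% | 16/700 = 2.3% |
| 18 | 14/682 = 2.1% | 14/700 = 2.0% | 32/700 = 4.6% |
| 18 | 48/682 = 7.0% | 48/700 = 6.9% | 66/700 = 9.4% |
| 18 | 150/682 = 22.0% | 150/700 = 21.4% | 168/700 = 24.0% |

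A milder case is k = 5 and m = 1. The overall rate goes from 14/695 = 2.01% to 15/700 = 2.14%. If all 695 others count in the period, the by-period rate goes from 14/695 = 2.01% to 15/696 = 2.16%. At a common-event rate, the same restored patient lowers the overall rate slightly: 153/695 = 22.01% becomes 154/700 = 22.00%.

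**The case against.** The strongest reply is that nobody is shown to be excluded. The population definition does not say post-baseline; the phrase stands only in a table shell. With Baseline in the parent trial and every patient a Week 12 completer, the row is empty. Assessment is undefined, and protocol Section 15 counts adverse event reporting among the means of assessing safety, so a recorded event may itself qualify. Early terminators are meant to complete all Week 40 procedures. Exclusions would be visible in Tables 14.0.1 and 14.0.2.1 and Listing 16.2.3, and the serious adverse event listing is not restricted by title to the Safety Population.

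Much of this stands. It shows that the effect is conditional and probably small. It does not rescue the condition: if the literal reading is right, the condition does nothing, and if the other is right, it selects on post-dosing behaviour. Two programmers could derive different populations. Visible counts of exclusions do not put events back into the tables.

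A reader might infer more: that any patient who reacts and never returns leaves both numerator and denominator, and that the bias always flatters the product. The documents do not support this.

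- A reaction never reported is in no numerator under any definition, and restoring that patient only enlarges the overall denominator.
- A patient who returns neither diary nor pump may already fail the confirmed-dose condition.
- The telephone reporting in protocol Sections 16.5, 16.7 and 16.8 runs from site to sponsor, so it is not evidence of patients phoning in events. Section 16.4 is the better support.

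**Conclusion.** The point holds in a limited form. The condition is redundant for rollovers or, read as post-dosing, can omit a former vehicle patient with documented use, a reported event and no later visit. The direction is clear only in the by-period tables; in the overall tables it depends on whether the excluded patients have reported events more often than those kept.

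The number affected cannot be derived from the documents. The 2 to 18 patients without a later visit rest on assumed shares, and those with documented use and a reported event are fewer, plausibly none to a few. The largest shift shown, about 2.5 percentage points (4.57% − 2.05%), requires 18 excluded patients who all had events and should not be read as an estimate. For common events the effect is negligible. For a rare event one omitted case could matter, which justifies a correction before database lock.

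**What to change.** - In SAP 8.4.1, define the Safety Population as all enrolled patients with at least one application of S5G4T-1, presuming use after dispensing unless non-use is documented. The presumption matters: without it, a patient who returns no diary or pump could still be excluded.
- Delete the assessment condition and its row in Table 14.0.2.1, and reword the remaining row to match the presumption of use.
- Keep the observed n at each visit for dryness, scaling, itching and burning/stinging; these shells already show it.
- Record the departure from protocol 18.2 and the synopsis in SAP Section 10. The SAP preface allows updates until database lock.

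No new data are needed. The cost is a few lines of text and programming. The small downside is that a few patients without follow-up, possibly including some who never applied the product, enter the overall denominators and may slightly dilute overall rates.

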8.5 Demographic and Other Baseline Characteristics

All baseline summaries will be done on the Safety population.

Sex (categorical), race (categorical), and ethnicity (categorical) will be summarized by counts and percentages. Age (continuous), height (cm) (continuous), and weight (kilograms (kg)) (continuous), and body mass index (BMI) (continuous) will be summarized with descriptive statistics.

Age will be calculated as the difference in days between the date of birth and the date of informed consent and converted to years by dividing the number of days by 365.25 and using a floor function to drop the decimal portion. In case the exact birth day is missing, day 15 will be used. The BMI will be calculated as weight (kg) divided by squared height (m²).

Medical histories will be coded using the Medical Dictionary for Regulatory Activities (MedDRA) dictionary and presented in a by-subject listing. All medical history for rollover subjects will be entered into 54-07 database and therefore medical history data will not be pulled from the 54-01 or 54-02 studies. The date of rosacea diagnosis for rollover subjects will be pulled from the 54-01 or 54-02 study.

The medical history data will be summarized with frequencies and percentages of patients with at least one medical history term reported, and patient frequencies and percentages on the System

Organ Class (SOC) and Preferred Term levels. The number of events will also be summarized. The table will be sorted by overall descending frequency of SOC and then, within a SOC, by overall descending frequency of Preferred Term.

8.6 Prior and Concomitant Medications

Concomitant medications will be coded to preferred name and Anatomical Therapeutic Chemical (ATC) classification of ingredients using the World Health Organization (WHO) Drug Global Dictionary, Format B3, Version March 1, 2018. Ongoing medications for rollover subjects will be entered into 54-07. Only medications that are not ongoing in 54-01 or 54-02 will be pulled forward for subjects who received S5G4T-1 in 54-01 or 54-02.

Medications which start prior to first application of S5G4T-1 (from 54-01/02 or 54-07) will be considered prior medications. Ongoing medications and medications ending after the date of first application (in 54-01/02 or 54-07) will be considered concomitant medications. If the date of first application is unknown and the medication is not listed as ongoing the interval will be considered “unknown”. If the date of first application is unknown and the medication is listed as ongoing the interval will be considered concomitant.

Incomplete medication start and end dates will be imputed as described in Section [8.1.5.1](#).

A by-subject listing of all prior and concomitant medications will be presented for the Safety population.

8.7 Prior and Concomitant Procedures/Therapies

Procedures/therapies will be coded using the MedDRA dictionary. Ongoing procedures/therapies for rollover subjects will be entered into 54-07. Only procedures/therapies that are not ongoing in 54-01 or 54-02 will be pulled forward for subjects who received S5G4T-1 in 54-01 or 54-02.

Procedures/therapies which start prior to first application of S5G4T-1 (from 54-01/02 or 54-07) will be considered prior procedures/therapies. Ongoing procedures/therapies and procedures/therapies ending after the date of first application (in 54-01/02 or 54-07) will be considered concomitant procedures/therapies. If the date of first application is unknown and the procedures/therapies is not listed as ongoing the interval will be considered “unknown”. If the date of first application is unknown and the procedures/therapies is listed as ongoing the interval will be considered concomitant.

Incomplete procedures/therapies start and end dates will be imputed as described in Section [8.1.5.1](#).

A by-subject listing of all prior and concomitant procedure/therapies will be presented for the Safety population.

8.8 Analysis of Efficacy

All efficacy analysis will be conducted on the Safety population.

8.8.1 IGA

Descriptive statistics will be used to summarize the assessment of efficacy. IGA scores will be summarized at Baseline (see definition of baseline in Section 8.1.2) and every 4 weeks through end of the study. The number and percentage of patients who achieve treatment success at the scheduled study visits will be tabulated. A patient will be considered a success if their IGA score is clear or almost clear.

In addition to the above summary a by-subject listing of all IGA results will be presented.

